6.3.2.2 Visit 4 (Week 1)

The following procedures will be performed at Visit 4 (Week 1):

- Collect blood to evaluate serum for ADAs and to measure exploratory biomarkers (from patients who have consented to the procedure);
- Assess AEs;
- Perform physical examination;
- Measure vital signs;
- Perform clinical laboratory tests;
- Perform triplicate 12-lead ECGs; and
- Perform urinalysis for kidney biomarkers and for microscopic evaluation of sediment.

6.3.2.3 Visit 5 (Week 2)

The following procedures will be performed at Visit 5 (Week 2):

- Assess AEs;
- Perform physical examination;
- Measure vital signs; and
- Perform clinical laboratory tests.

6.3.2.4 Visit 6 (Week 3)

The following procedures will be performed at Visit 6 (Week 3):

- Record prior and concomitant medications, including information on any thyroid-blocking drugs;
- Deliver thyroid-blocking drugs for next visit;

Note: Patients will not take the thyroid-blocking drugs at this visit but will be instructed to take them 24 hours prior to their next visit (ie, 24 hours prior to study drug administration).

- Assess AEs;
- Perform physical examination;
- Measure vital signs;
- Perform clinical laboratory tests;

- Perform triplicate 12-lead ECGs; and
- Perform urinalysis for kidney biomarkers and for microscopic evaluation of sediment.

6.3.2.5 Visit 7 (Week 4)

Dose 2 of Cycle 1 will be administered at Visit 7. The following procedures will be performed at Visit 7 (Week 4):

- Admit to radioactive unit for hospitalization prior to study drug administration;

Note: Patients will be admitted during each IV administration for a total of 48 hours. This hospitalization can be shortened if ^{131}I decay and the patient's clearance allow discharge according to the applicable local regulations on radioactive compound exposure.

Note: Before the patient is released, a leaflet containing information on radioprotection rules and general precautions after radiation treatment will be distributed (see [Appendix F](#)).

- Confirm the ingestion of thyroid-blocking drugs at least 24 hours prior to study drug administration;
- Deliver and confirm the ingestion of thyroid-blocking drugs 1 hour prior to study drug administration;
- Deliver and confirm the ingestion of thyroid-blocking drugs 24 and 48 hours after study drug administration;

Note: If the patient is discharged prior to 48 hours, deliver the thyroid-blocking drugs for 48 hours at 24 hours. Patients will still take the thyroid-blocking drugs 48 hours after study drug administration.

- Perform urine hCG testing in all female patients of childbearing potential (ie, ovulating, premenopausal, and not surgically sterile) prior to study drug administration;
- Collect blood to evaluate serum for ADAs and to measure exploratory biomarkers (from patients who have consented to the procedure) prior to study drug administration;
- Assess AEs;
- Perform physical examination prior to study drug administration and at 24 hours after study drug administration;
- Measure vital signs prior to study drug administration and 30 minutes, 5 hours, 24 hours, and 48 hours after study drug administration;
- Perform clinical laboratory tests prior to study drug administration;
- Administer anti-emetic, anti-histamine, and anti-pyretic premedication therapy approximately 30 minutes prior to the start of the amino acid infusion, according to the site's standard operating procedures;
- Administer saline 0.9% infusion, starting 30 minutes prior to study drug administration and continuing for up to 3 hours after, at a rate of 200 to 300 mL/hour;
- Administer an amino acid solution beginning 30 minutes prior to study drug administration and ending 3 hours after study drug administration at a rate of 250 to 500 mL/hour;

- Administer study drug via slow IV infusion, ie, administer using a shielded infusion device over approximately 3 to 30 minutes, depending on the volume to be injected; and
- Perform a planar WB scan and a SPECT/CT scan 24 (± 4) hours after study drug administration.

6.3.2.6 Visit 8 (Week 5)

The following procedures will be performed at Visit 8 (Week 5):

- Assess AEs;
- Perform physical examination;
- Measure vital signs;
- Perform clinical laboratory tests;
- Perform triplicate 12-lead ECGs; and
- Perform urinalysis for kidney biomarkers and for microscopic evaluation of sediment.

6.3.2.7 Visit 9 (Week 6)

The following procedures will be performed at Visit 9 (Week 6):

- Assess AEs;
- Perform physical examination;
- Measure vital signs; and
- Perform clinical laboratory tests.

6.3.2.8 Visit 10 (Week 8)

The following procedures will be performed at Visit 10 (Week 8):

- Collect blood to evaluate serum for ADAs and to measure exploratory biomarkers (from patients who have consented to the procedure);
- Assess AEs;
- Perform physical examination;
- Measure vital signs;
- Perform clinical laboratory tests;

Note: Clinical laboratory tests should be performed prior to any imaging.

- Perform triplicate 12-lead ECGs;
- Perform urinalysis for kidney biomarkers and for microscopic evaluation of sediment;
- Assess performance status using the ECOG PS; and
- Perform imaging to evaluate disease status.

Note: Diagnostic CT scan will be performed in all patients. Brain MRI will only be performed in patients with known brain metastases.

6.3.2.9 Visit 11 (Week 11): End of Treatment Visit or Cycle 2 eligibility assessment

This visit will also serve as the eligibility assessment for Cycle 2 of the dose expansion phase. Cycle 2 eligibility will be assessed by evaluating disease state and safety. This visit will serve as the EOT Visit for patients who do not see CB.

The following procedures will be performed at Visit 11 (Week 11):

- Update demographics and medical history, including confirmation of lesion size;
- Record prior and concomitant medications, including information on any thyroid-blocking drugs;
- Deliver thyroid-blocking drugs for next visit (only patients eligible for and continuing to Cycle 2);

Note: Patients will not take the thyroid-blocking drugs at this visit but will be instructed to take them 24 hours prior to their next visit (ie, 24 hours prior to study drug administration).

- Perform urine hCG testing in all female patients of childbearing potential (ie, ovulating, premenopausal, and not surgically sterile);
- Collect blood to evaluate serum for ADAs and to measure exploratory biomarkers (from patients who have consented to the procedure);
- Assess AEs;
- Measure weight;
- Perform physical examination;
- Measure vital signs;
- Perform clinical laboratory tests;

Note: Clinical laboratory tests should be performed prior to any imaging.

- Perform triplicate 12-lead ECGs;
- Perform echocardiogram;

Note: LVEF may alternatively be measured using a multigated acquisition scan.

- Perform urinalysis for kidney biomarkers and for microscopic evaluation of sediment; and
- Perform imaging to evaluate disease status (EOT Visit only).

Note: Diagnostic CT scan will be performed in all patients. Brain MRI will only be performed in patients with known brain metastases.

Note: If the patient is continuing to Cycle 2, imaging to evaluate disease status will not be performed.

6.3.3 Cycle 2 of the Dose Expansion Phase

6.3.3.1 Visit 11 (Cycle 2 eligibility assessment)

See the list of procedures for Visit 11 (Week 11) in Cycle 1 of the dose expansion phase in [Section 6.3.2.9](#).

6.3.3.2 Visit 12 (Week 0)

Dose 1 of Cycle 2 will be administered at Visit 12. Visit 12 will occur at approximately 2 weeks after Visit 11. The following procedures will be performed at Visit 12 (Week 0):

- Admit to radioactive unit for hospitalization prior to study drug administration;

Note: Patients will be admitted during each IV administration for a total of 48 hours. This hospitalization can be shortened if ^{131}I decay and the patient's clearance allow discharge according to the applicable local regulations on radioactive compound exposure.

Note: Before the patient is released, a leaflet containing information on radioprotection rules and general precautions after radiation treatment will be distributed (see [Appendix F](#)).

- Confirm the ingestion of thyroid-blocking drugs at least 24 hours prior to study drug administration;
- Deliver and confirm the ingestion of thyroid-blocking drugs 1 hour prior to study drug administration;
- Deliver and confirm the ingestion of thyroid-blocking drugs 24 and 48 hours after study drug administration;

Note: If the patient is discharged prior to 48 hours, deliver the thyroid-blocking drugs for 48 hours at 24 hours. Patients will still take the thyroid-blocking drugs 48 hours after study drug administration.

- Perform urine hCG testing in all female patients of childbearing potential (ie, ovulating, premenopausal, and not surgically sterile) prior to study drug administration;
- Assess AEs;
- Perform physical examination prior to study drug administration and at 24 hours after study drug administration;
- Measure vital signs prior to study drug administration and 30 minutes, 5 hours, 24 hours, and 48 hours after study drug administration;
- Administer anti-emetic, anti-histamine, and anti-pyretic premedication therapy approximately 30 minutes prior to the start of the amino acid infusion, according to the site's standard operating procedures;
- Administer saline 0.9% infusion, starting 30 minutes prior to study drug administration and continuing for up to 3 hours after, at a rate of 200 to 300 mL/hour;
- Administer an amino acid solution beginning 30 minutes prior to study drug administration and ending 3 hours after study drug administration at a rate of 250 to 500 mL/hour;

- Administer study drug via slow IV infusion, ie, administer using a shielded infusion device over approximately 3 to 30 minutes, depending on the volume to be injected; and
- Perform a planar WB scan 24 (± 4) hours after study drug administration. The planar WB scan done at this visit will also serve as the PD distribution scan.

6.3.3.3 Visit 13 (Week 1)

The following procedures will be performed at Visit 13 (Week 1):

- Collect blood to evaluate serum for ADAs and to measure exploratory biomarkers (from patients who have consented to the procedure);
- Assess AEs;
- Perform physical examination;
- Measure vital signs;
- Perform clinical laboratory tests;
- Perform triplicate 12-lead ECGs; and
- Perform urinalysis for kidney biomarkers and for microscopic evaluation of sediment.

6.3.3.4 Visit 14 (Week 2)

The following procedures will be performed at Visit 14 (Week 2):

- Assess AEs;
- Perform physical examination;
- Measure vital signs; and
- Perform clinical laboratory tests.

6.3.3.5 Visit 15 (Week 3)

The following procedures will be performed at Visit 15 (Week 3):

- Record prior and concomitant medications, including information on any thyroid-blocking drugs;
- Deliver thyroid-blocking drugs for next visit;

Note: Patients will not take the thyroid-blocking drugs at this visit but will be instructed to take them 24 hours prior to their next visit (ie, 24 hours prior to study drug administration).

- Assess AEs;
- Perform physical examination;
- Measure vital signs;
- Perform clinical laboratory tests;
- Perform triplicate 12-lead ECGs; and
- Perform urinalysis for kidney biomarkers and for microscopic evaluation of sediment.

6.3.3.6 Visit 16 (Week 4)

Dose 2 of Cycle 2 will be administered at Visit 16 (Week 4). The following procedures will be performed at Visit 16 (Week 4):

- Admit to radioactive unit for hospitalization prior to study drug administration;

Note: Patients will be admitted during each IV administration for a total of 48 hours. This hospitalization can be shortened if ^{131}I decay and the patient's clearance allow discharge according to the applicable local regulations on radioactive compound exposure.

Note: Before the patient is released, a leaflet containing information on radioprotection rules and general precautions after radiation treatment will be distributed (see [Appendix F](#)).

- Confirm the ingestion of thyroid-blocking drugs at least 24 hours prior to study drug administration;
- Deliver and confirm the ingestion of thyroid-blocking drugs 1 hour prior to study drug administration;
- Deliver and confirm the ingestion of thyroid-blocking drugs at least 24 and 48 hours after study drug administration;

Note: If the patient is discharged prior to 48 hours, deliver the thyroid-blocking drugs for 48 hours at 24 hours. Patients will still take the thyroid-blocking drugs 48 hours after study drug administration.

- Perform urine hCG testing in all female patients of childbearing potential (ie, ovulating, premenopausal, and not surgically sterile) prior to study drug administration;
- Collect blood to evaluate serum for ADAs and to measure exploratory biomarkers (from patients who have consented to the procedure) prior to study drug administration;
- Assess AEs;
- Perform physical examination prior to study drug administration and at 24 hours after study drug administration;
- Measure vital signs prior to study drug administration and 30 minutes, 5 hours, 24 hours, and 48 hours after study drug administration;
- Perform clinical laboratory tests prior to study drug administration;
- Administer anti-emetic, anti-histamine, and anti-pyretic premedication therapy approximately 30 minutes prior to the start of the amino acid infusion, according to the site's standard operating procedures;
- Administer saline 0.9% infusion, starting 30 minutes prior to study drug administration and continuing for up to 3 hours after, at a rate of 200 to 300 mL/hour;
- Administer an amino acid solution beginning 30 minutes prior to study drug administration and ending 3 hours after study drug administration at a rate of 250 to 500 mL/hour;

- Administer study drug via slow IV infusion, ie, administer using a shielded infusion device over approximately 3 to 30 minutes, depending on the volume to be injected; and
- Perform a planar WB scan 24 (± 4) hours after study drug administration.

6.3.3.7 Visit 17 (Week 5)

The following procedures will be performed at Visit 17 (Week 5):

- Assess AEs;
- Perform physical examination;
- Measure vital signs;
- Perform clinical laboratory tests;
- Perform triplicate 12-lead ECGs; and
- Perform urinalysis for kidney biomarkers and for microscopic evaluation of sediment.

6.3.3.8 Visit 18 (Week 6)

The following procedures will be performed at Visit 18 (Week 6):

- Assess AEs;
- Perform physical examination;
- Measure vital signs; and
- Perform clinical laboratory tests.

6.3.3.9 Visit 19 (Week 8)

The following procedures will be performed at Visit 19 (Week 8):

- Collect blood to evaluate serum for ADAs and to measure exploratory biomarkers (from patients who have consented to the procedure);
- Assess AEs;
- Perform physical examination;
- Measure vital signs;
- Perform clinical laboratory tests;

Note: Clinical laboratory tests should be performed prior to any imaging.

- Perform triplicate 12-lead ECGs;
- Perform urinalysis for kidney biomarkers and for microscopic evaluation of sediment;
- Assess performance status using the ECOG PS; and
- Perform imaging to evaluate disease status.

Note: Diagnostic CT scan will be performed in all patients. Brain MRI will only be performed in patients with known brain metastases.

6.3.3.10 Visit 20 (Week 11): End of Treatment Visit

The following procedures will be performed at Visit 20 (Week 11/EOT Visit):

- Record prior and concomitant medications, including information on any thyroid-blocking drugs;
- Perform urine hCG testing in all female patients of childbearing potential (ie, ovulating, premenopausal, and not surgically sterile);
- Collect blood to evaluate serum for ADAs and to measure exploratory biomarkers (from patients who have consented to the procedure);
- Assess AEs;
- Measure weight;
- Perform physical examination;
- Measure vital signs;
- Perform clinical laboratory tests;

Note: Clinical laboratory tests should be performed prior to any imaging.

- Perform triplicate 12-lead ECGs;
- Perform echocardiogram;

Note: LVEF may alternatively be measured using a multigated acquisition scan.

- Perform urinalysis for kidney biomarkers and for microscopic evaluation of sediment; and
- Perform imaging to evaluate disease status.

Note: Diagnostic CT scan will be performed in all patients. Brain MRI will only be performed in patients with known brain metastases.

6.4 Early Termination Visit and Withdrawal Procedures

For patients who receive at least 1 dose of study drug, but are withdrawn from the study prior to completion, all assessments scheduled for the last visit in the cycle (ie, Week 11) should be performed at an ET Visit.

Patients will continue into the long-term follow-up period after ET or withdrawal so that post-treatment therapy can be monitored.

6.5 Long-Term Follow-Up Period and End of Study

A long-term follow-up period will start after the EOT/ET Visit. Follow-up will continue for a maximum of 12 months. All patients without disease progression will be monitored every 8 weeks to evaluate PFS for a maximum of 12 months or until disease progression, death, or consent is withdrawn, whichever occurs first.

The bi-monthly visits will consist of imaging to evaluate disease status, performance status evaluation using ECOG PS, and assessment for any post-investigational treatment. Other changes in medical history or concomitant medications and AEs will be assessed. Imaging to evaluate

disease status will begin 8 weeks after the last diagnostic CT scan or brain MRI performed during the study treatment period. Diagnostic CT scan will be performed in all patients. Brain MRI will only be performed in patients with known brain metastases. Patients with extracranial lesions will be evaluated for progression using RECIST version 1.1. Patients with brain metastases without extracranial lesions will be evaluated for progression using RANO-BM. Patients with extracranial lesions and brain metastases will be evaluated for progression using both RECIST version 1.1 (extracranial lesions) and RANO-BM (brain metastases). Additional details are provided in the Imaging Review Charter. As long as there is no disease progression, imaging to evaluate disease status will be performed every 8 weeks.

For patients with disease progression or starting alternative anticancer therapy, imaging to evaluate disease status will be performed according to the local site standard of care. Review of images at this point will be done locally and not by the central imaging core laboratory. Additionally, those patients will no longer be followed every 8 weeks, but every 12 weeks, to assess survival, disease status, and post-progression therapy. Follow-up contacts (by clinic visits or telephone call) will be performed every 12 weeks until death, lost to follow-up, study end (12 months post-last patient EOT/ET Visit), or study termination by the Sponsor, whichever occurs first.

7 EFFICACY AND DOSIMETRY VARIABLES

7.1 Primary Efficacy Variables

The primary efficacy endpoints are as follows:

- Proportion of patients achieving an objective response (CR or PR) with the use of CAM-H2 as measured by RECIST version 1.1 (all patients with extracranial lesions) or as measured by RANO-BM (patients with brain metastases without extracranial lesions); and
- CBR of CAM-H2 using the equation $CBR = CR + PR + SD$, as measured by RECIST version 1.1 (all patients with extracranial lesions) or as measured by RANO-BM (patients with brain metastases without extracranial lesions).

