For the dosimetry study, defined critical organs (ie, the kidneys and liver) and target lesions (ie, lesions representative of the extent of disease and deemed avid at the discretion of the central reviewer, based on qualitative visual assessment) will be delineated on planar WB scans and/or SPECT/CT scans. Further details are provided in the Imaging Review Charter.

The percentage of injected activity (%IA) will be calculated in each set of images as the ratio between the measured activity in the lesion and the total injected activity as a function of time to derive the absorbed dose. Organ time-activity curves will be generated by plotting %IA versus time to derive the absorbed dose.

Tumor dosimetry in tumor lesions will be calculated based on the consecutive SPECT/CT and/or planar WB scans during Cycle 1 of the dose escalation phase.

EFFICACY VARIABLES:

The primary efficacy endpoints are as follows:

- Proportion of patients achieving an objective response (CR or PR) with the use of CAM-H2 as measured by RECIST version 1.1 (all patients with extracranial lesions) or as measured by RANO-BM (patients with brain metastases without extracranial lesions); and
- CBR of CAM-H2 using the equation $CBR = CR + PR + SD$, as measured by RECIST version 1.1 (all patients with extracranial lesions) or as measured by RANO-BM (patients with brain metastases without extracranial lesions).

The secondary efficacy endpoints are as follows:

- PFS for patients receiving CAM-H2;
- DoR in patients receiving CAM-H2;
- PFS in patients with brain metastases receiving CAM-H2;
- OS for patients receiving CAM-H2; and
- Proportion of patients on CAM-H2 who develop ADAs.

DOSIMETRY VARIABLES:

The dosimetry endpoint consists of dosimetry for CAM-H2 via SPECT/CT and planar WB scans. Endpoints will include the biodistribution and PD profile of CAM-H2 dosimetry results for target lesions based on region of interest.

SAFETY VARIABLES:

Safety and tolerability will be assessed during the study and will include the following:

- Incidence and severity of treatment-emergent adverse events;
- MTD of CAM-H2;
- DLT rate of CAM-H2;
- RDP2 for CAM-H2;
- Physical examinations, including full neurologic examinations, as well as assessments of general appearance, skin, eyes, ears, nose, throat, neck, lymph nodes, chest, heart (including auscultation for heart sounds and murmurs), abdomen, extremities, and musculoskeletal systems;

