3.1.1.3 Imaging

All imaging will be sent to the central imaging core laboratory for independent review as soon as possible within 48 hours of acquisition. Further instructions will be provided by the imaging core laboratory in separate guidelines.

Patients will undergo 4 types of imaging during the dose escalation phase: planar whole body (WB) scans, single photon emission computed tomography (SPECT)/CT scans, diagnostic CT scans, and brain MRI scans, as shown in [Table 1](#). Imaging to evaluate the organ/target lesion uptake will be performed after each CAM-H2 administration during the dose escalation phase of

the study for all patients at all dose levels. Dosimetry in tumor lesions, calculated based on consecutive SPECT/CT and planar WB scans, will be performed during Cycle 1. To evaluate disease progression, diagnostic CT scans will be performed in all patients, and brain MRI will only be performed in patients with known brain metastases. Patients with extracranial lesions will be evaluated for progression using RECIST version 1.1. Patients with brain metastases without extracranial lesions will be evaluated for progression using RANO-BM. Patients with extracranial lesions and brain metastases will be evaluated for progression using both RECIST version 1.1 (extracranial lesions) and RANO-BM (brain metastases). Additional details are provided in the Imaging Review Charter.

Table 1. Imaging During the Dose Escalation Phase

Type of Imaging	Cycle 1	Cycles 2, 3, and 4
Planar WB scans for PD distribution [1], evaluation of organ/target lesion uptake, and/or dosimetry	
After each dose (Dose 1 and Dose 2):
 
 • 5 hours (± 1 hour) after CAM-H2 [2]; • 24 hours (± 4 hours) after CAM-H2; • 48 hours (± 4 hours) after CAM-H2; and • 168 hours (± 24 hours) after CAM-H2. 	After each dose (Dose 1 and Dose 2): • 24 hours (± 4 hours) after CAM-H2 [2].
SPECT/CT scans to evaluate organ/target lesion uptake and/or dosimetry	
After each dose (Dose 1 and Dose 2):
 
 • 5 hours (± 1 hour) after CAM-H2; • 24 hours (± 4 hours) after CAM-H2; • 48 hours (± 4 hours) after CAM-H2; and • 168 hours (± 24 hours) after CAM-H2. 	NA

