7.4 Efficacy Assessments

7.4.1 Objective Response

The proportion of patients achieving an objective response will be measured using RECIST version 1.1 (see [Appendix D](#)) or RANO-BM (see [Appendix E](#)). All patients with extracranial lesions will be evaluated for progression using RECIST version 1.1. Patients without extracranial lesions will be evaluated for progression using RANO-BM.

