7.4.2 Clinical Benefit Rate

The CBR will be measured using the equation $CBR = CR + PR + SD$, as measured by both RECIST version 1.1 (see [Appendix D](#)) and RANO-BM (see [Appendix E](#)). All patients with extracranial lesions will be evaluated for progression using RECIST version 1.1. Patients without extracranial lesions will be evaluated for progression using RANO-BM.

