9.2 Statistical Methods

9.2.1 Analysis of Efficacy

Efficacy analyses will be performed on the FAS. Overall response rate (ORR) will be assessed for each patient as well as the CBR, DoR, and PFS. A water-plot analysis of breast cancer and gastric/GEJ cancer populations will be done. Response magnitude, including CR and near-CR (defined as a >90% confirmed tumor volume reduction) will also be considered.

The primary and secondary efficacy variables are described in [Sections 7.1](#) and [7.2](#), respectively.

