9.2.4 Sample Size Determination

The proposed study is a dose escalation (Phase 1) study with an expansion cohort reaching into dose expansion (Phase 2). No formal sample size calculation was performed for dose escalation (Phase 1) of the study. A maximum of 18 patients are planned for dose escalation.

No formal sample size calculation was performed for dose expansion (Phase 2). However, a planned sample size of 52 patients is deemed sufficient to obtain an initial estimate of response rates to formally power a subsequent Phase 2/3 study.

For each indication (ie, breast, gastric, or GEJ cancer), an interim evaluation of efficacy will be conducted when approximately 50% of patients complete Cycle 1 at the recommended dose for expansion based on objective responses determined from RECIST 1.1 or RANO-BM. One analysis will be performed for patients with breast cancer, and another analysis will be performed for patients with gastric or GEJ cancer. If the ORR is <10% for a specific indication (ie, breast or gastric/GEJ), the study will be terminated for that particular indication.

The Statistical Analysis Plan will provide more details on the exact statistical approach.

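### For patients with both extracranial lesions and brain metastases, the response rule (ORR, CBR) and the progression rule (PFS) do not match, and no page reviewed says how the RECIST and RANO-BM reads combine

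*Combined protocol and SAP*

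**What the plan says.** **Response.** Section 7.1 measures ORR and CBR "as measured by RECIST version 1.1 (all patients with extracranial lesions) or as measured by RANO-BM (patients with brain metastases without extracranial lesions". The synopsis and Section 2.1 use the same allocation. RANO-BM is named only for patients who have no extracranial disease.

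**Progression.** Section 3.1.1.3 adds a rule for patients with both sites: "Patients with extracranial lesions and brain metastases will be evaluated for progression using both RECIST version 1.1 (extracranial lesions) and RANO-BM (brain metastases". Sections 3.1.3 and 6.5 and the matching synopsis paragraphs repeat it, and Section 3.1.2.3 carries it into the expansion phase by cross-reference.

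**Efficacy assessments.** Section 7.4.1 states "All patients with extracranial lesions will be evaluated for progression using RECIST version 1.1" and gives RANO-BM to patients without extracranial lesions. It has no sentence for patients with both sites. Section 7.4.2 has the same two sentences, but it introduces CBR "as measured by both RECIST version 1.1" and RANO-BM, where Section 7.1 joins the two criteria with *or*.

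**Analysis.** Section 9.2.1 says "Overall response rate (ORR) will be assessed for each patient as well as the CBR, DoR, and PFS" and names no criterion. The PFS objective in Section 2.2 names none either. The interim rule in Section 9.2.4 is "based on objective responses determined from RECIST 1.1 or RANO-BM".

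**The concern.** ORR and CBR carry the efficacy conclusion of the expansion phase. The design deliberately recruits breast cancer patients with measurable brain metastases (at least 10 to 12, Section 3.1.2.1) and gives patients with brain metastases their own PFS endpoint (Section 7.2). Those among them who also have extracranial disease are the patients for whom the two rules part.

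Read literally, the same visit can be scored as a success for a primary endpoint and as a failure for PFS. DoR has the same difficulty, because it needs both a response rule and a progression rule. In long-term follow-up, imaging after progression moves to local practice: "Review of images at this point will be done locally and not by the central imaging core laboratory". A RECIST response in a patient already counted as progressed in the brain would then no longer be followed on the central 8-week schedule.

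The study is open label. If the rule is not written down beforehand, it would be settled after individual results are known.

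**Working it through.** **1. The passages side by side, for a patient with both sites**

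- Sections 3.1.1.3, 3.1.3 and 6.5 (progression): RECIST for extracranial lesions and RANO-BM for brain metastases.
- Section 7.1 (ORR, CBR): RECIST, because the patient has extracranial lesions.
- Section 7.4.1 (objective response): RECIST; the sentence requiring both criteria is missing.
- Section 7.4.2 (CBR): opens with both criteria, then assigns RECIST; the sentence for patients with both sites is missing.
- Section 9.2.1: no criterion named.

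**2. If RECIST covers extracranial lesions only**

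This is how Sections 3.1.1.3, 3.1.3 and 6.5 label it. Take extracranial PR or SD on CT and RANO-BM progression on MRI at the same visit. Section 7.1 gives a response or clinical benefit. Section 6.5 gives progression, and so a PFS event.

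**3. If RECIST also counts brain lesions**

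Appendix D sets no site limit on target or new lesions. New brain lesions, or unequivocal progression of non-target brain lesions, would then be RECIST PD, and for those the conflict disappears. It can remain for measured brain lesions. Illustration with assumed sizes (extracranial sum 80 mm, one brain target lesion of 20 mm that grows to 26 mm):

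- RANO-BM (Table 13): 26/20 − 1 = +30%, and +6 mm. Both progression conditions (20% and 5 mm) are met: PD.
- Combined RECIST sum, extracranial unchanged: 80 + 20 = 100 mm to 80 + 26 = 106 mm, +6%: SD (Table 12).
- Combined RECIST sum, extracranial falling to 40 mm: 100 mm to 40 + 26 = 66 mm, −34%: PR.

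**4. Scale**

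Inputs from the protocol: 52 patients (Section 9.2.4) and at least 10 to 12 breast cancer patients with measurable brain metastases (Section 3.1.2.1). The number with both sites is not given.

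- Share of the planned total: 10/52 = 19.2%; 12/52 = 23.1%.
- One reclassified patient: 1/52 = 1.9 points.

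Assume that all 10 to 12 have both sites and that 10% to 25% of them have brain progression at the visit that would otherwise qualify as PR or SD:

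- CBR: 10 × 0.10 = 1.0 patient (1.9 points) to 12 × 0.25 = 3.0 patients (5.8 points).
- ORR, if 20% of those patients have an extracranial response (also assumed): 0.2 to 0.6 patients, or 0.4 to 1.2 points.

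For comparison, the exact 95% interval for 13/52 (25%) runs from 14.0% to 38.9%.

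**5. Interim rule (stop an indication if ORR is below 10%)**

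The smallest number of responders that allows an indication to continue is 1 for n up to 10, 2 for n = 11 to 20 and 3 for n = 21 to 30. The interim n per indication is not stated. With an assumed n = 13, 1/13 = 7.7% stops and 2/13 = 15.4% continues. One reclassified patient matters only when the count is at that boundary.

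**The case against.** A reader might infer that the protocol flatly contradicts itself and prescribes RECIST alone for these patients. The text does not go that far. The word *alone* does not appear. Section 6.5 contains nearly the same two sentences as Sections 7.4.1 and 7.4.2 and then adds the rule for patients with both sites, so the authors evidently saw these statements as compatible. Sections 7.4.1 and 7.4.2 leave that rule out; they do not deny it. Section 7.1 set against Section 3.1.1.3 is a difference between a response rule and a progression rule, which is a mismatch between endpoints and not two opposing statements about one endpoint. For CBR, Section 7.4.2 even names both criteria.

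A reader might also infer that no combining rule exists. That cannot be said. Sections 3.1.1.3, 3.1.3 and 6.5 refer to an Imaging Review Charter for details, and Section 9.2.4 leaves the exact statistical approach to the SAP. Neither the Charter nor separate SAP text was among the pages reviewed.

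Finally, the double scoring depends on RECIST excluding the brain, which Appendix D does not say, and the remaining example uses invented lesion sizes. The magnitudes rest on assumed rates. If best response is used (not stated), brain progression after an earlier response or SD changes neither ORR nor CBR.

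All of this stands, and it limits the point. It does not remove it: the protocol's own endpoint definitions allocate the criteria differently for the same patients, Sections 7.1 and 7.4.2 use different connectives for the same primary endpoint, and under the protocol's own labels the double scoring follows.

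**Conclusion.** The mismatch is real and should be corrected, but its numerical effect is probably small. The number of patients with both sites could be anywhere from 0 to about 12, or higher if more patients with brain metastases enrol or if gastric/GEJ patients have them. Each reclassified patient moves ORR or CBR by 1.9 points on 52. CBR is more exposed than ORR because SD counts towards it: 1.9 to 5.8 points against 0.4 to 1.2 points under the assumed rates, both small beside the sampling uncertainty in 52 patients. The interim decision is affected only at the boundary. A reader might take this as evidence that the primary endpoints are materially inflated; the documents do not support that. The point is that a primary endpoint and PFS can disagree about one visit, and that the pages reviewed do not say which read prevails.

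**What to change.** In the synopsis and Sections 2.1, 7.1, 7.4.1 and 7.4.2, state that for patients with both extracranial lesions and brain metastases, an assessment with PD by either RECIST 1.1 or RANO-BM is overall PD for endpoint purposes. It is then neither a response nor SD at that assessment, and it does not erase an earlier valid response. Apply the same rule to ORR, CBR, DoR, PFS and the interim analysis. Add the sentence requiring both criteria (Sections 3.1.1.3 and 6.5) to Sections 7.4.1 and 7.4.2, reconcile *or* in Section 7.1 with *both* in Section 7.4.2, and align the Imaging Review Charter and SAP. This should be in place before the interim analysis.

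The cost is a text amendment with matching edits. The CT and brain MRI scans are already scheduled. The downside is that ORR and CBR stay the same or become slightly less favourable.

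This is an analysis rule only. The passages that use clinical benefit to allow further cycles (synopsis, Sections 3.1.1.2 and 3.1.2.2) must be reconciled with the endpoint definition; no clinical rule is proposed here.
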